7.7 Safety

7.7.1 Extent of Exposure

Duration of exposure will be listed for the Safety set with site 065-S and summarized using descriptive statistics for each treatment group for the Safety set, based on dosing records of the IMP medication on the eCRF. Duration of exposure will be calculated as follows:

Date of Last Study Drug Administration – Date of First Study Drug Administration + 1.

- treatment-related treatment-emergent serious AEs (TESAEs) by maximum severity (Grade 1, Grade 2, Grade 3, Grade 4, Grade 5)
- SAEs leading to death
- TESAEs leading to IMP treatment discontinuation
- TEAEs related to study procedures
- Treatment-emergent AESI's (Heart failure, Pitting edema, Bladder cancer, Bone fracture, Drug-induced liver injury – DILI)

The overview table will also summarize the number of events for the same categories in the Safety set.

Overview table for TEAEs will be repeated in the Safety set with site 065-S .

The number and percentage of patients reporting each pre-treatment AEs, TEAE, post-treatment AEs will be summarized by SOC and PT. Tables will be sorted by descending overall frequency of SOC. PTs will be sorted by descending overall total. The following summaries will be produced:

- Pre-treatment AEs, TEAEs, post-treatment AEs by SOC and PT
- TEAEs related to IMP treatment, by SOC and PT
- TEAEs causing discontinuation from IMP treatment, by SOC and PT
- TEAEs related to IMP treatment and causing discontinuation from IMP treatment, by SOC and PT
- TEAEs, by severity, SOC and PT
- Pre-treatment SAEs, TESAEs, post-treatment SAEs, by SOC and PT
- TESAEs related to IMP treatment, by SOC and PT
- Pre-treatment AEs, TEAEs, post-treatment AEs leading to death, by SOC and PT
- Pre-treatment AEs, TEAEs, post-treatment AESIs by SOC and PT

In the above summaries, patients with more than one AE within a particular SOC are counted only once for that SOC. Similarly, patients with more than one AE within a particular PT are counted only once for that PT. For summaries by maximum severity, patients with multiple AEs within a particular SOC or PT will be counted under the category of their most severe AE within that SOC or PT.

Additionally, the number and percent of each AE will be summarized for each treatment group, by descending overall frequency of SOC and PT (sorted by descending overall total), displaying the number of observed events for each PT.

Statistical Analysis Plan

Sponsor Name: Poxel
Sponsor Protocol ID: PXL065-003

TEAEs that are described as cardiovascular will also be summarized for each treatment group, by descending overall frequency of SOC and PT (sorted by descending overall total) displaying number of observed events for the Safety set.

Summary tables, will be repeated in the Safety set with site 065-S: for:

- TEAEs by SOC and PT
- TEAEs related to IMP treatment, by SOC and PT
- TESAEs by SOC and PT

7.7.2.1 Hypoglycemia

T2DM Patients are requested to immediately perform a finger stick glucose measurement with the self-monitoring blood glucose (SMBG) device provided for this study (unless CGM is used) if any symptoms occur that may be related to hypoglycemia and to avoid any delay in treating these symptoms. After the recovery of the symptoms, patients may report all the symptoms, date and time, dietary intake states, time of the recovery in the patient diary as well as blood glucose values if available.

Only symptoms and/or plasma glucose concentration values deemed by the Investigator to meet the definition of hypoglycemia should be reported on the AE section of the eCRF.

Hypoglycemia will be reported as recommended by the FDA guidance [2]:

- Probable symptomatic hypoglycemia: Hypoglycemia evidenced only by symptoms without blood glucose measurement
- Asymptomatic Hypoglycemia: Hypoglycemia evidenced only by plasma glucose concentration of less than 70 mg/dL (3.9 mmol/L) and not accompanied by typical symptoms of hypoglycemia
- Documented Symptomatic Hypoglycemia: Hypoglycemia evidenced both by typical symptoms and plasma glucose concentration of less than 70 mg/dL (3.9 mmol/L)
- Severe Hypoglycemia: Hypoglycemia requiring assistance of another person to administer carbohydrate or glucagon or other procedure

In case of AE of hypoglycemia, the Investigator should query the patient to understand the clinical context that may have explained a low glucose value (exercise, missing meal, timing of drug intake and SMBG). All these data should be reviewed by _____ Medical Monitor.

Summary tables of probable symptomatic hypoglycemia, asymptomatic hypoglycemia, documented symptomatic hypoglycemia and severe hypoglycemia by treatment group will be produced for the Safety set.

Hypoglycemic events will be hardcoded with SOC "Metabolism and nutrition disorders" and PT "Hypoglycaemia".

Hypoglycemia events will be listed for the Safety set with site 065-S ..

7.7.3 Laboratory Evaluations

All laboratory data will be reported in International System of Units (SI).

CONFIDENTIAL

Document Date: 12AUG2022

Page 39 of 56

Statistical Analysis Plan

Sponsor Name: Poxel
Sponsor Protocol ID: PXL065-003

Laboratory data will be summarized using standard descriptive statistics for each treatment group, by scheduled visit for the Safety population.

7.7.3.1 Standard Safety Laboratory Panel

Data for the following hematology, biochemistry, urinalysis and coagulation received from central laboratory will be listed for the Safety set with site 065-S and summarized by treatment group and visit for the Safety set. Local laboratory results will be listed only.

Hematology	Biochemistry	Urinalysis
Erythrocytes Hemoglobin Hematocrit Red Blood Cell Morphology Mean corpuscular volume Mean corpuscular hemoglobin Mean corpuscular hemoglobin concentration Leucocytes Differential blood count (lymphocytes, monocytes, eosinophils, basophils, neutrophils/ absolute values and percentages should be given) Thrombocytes	Blood Urea Nitrogen Creatinine Sodium Potassium Chloride Bicarbonate Calcium Inorganic phosphate Total protein Albumin Uric acid Creatine phosphokinase AST ALT GGT Total bilirubin ALP hsCRP TSH (during Screening Period only)	pH Specific gravity Protein Glucose Ketones Nitrites Urobilinogen Blood Leucocytes If the dipstick result is abnormal: microscopic examination of the sediment for blood cells, cylinders, etc.

Coagulation
Activated Partial Thromboplastin Time (aPTT) Prothrombin Time International Normalized Ratio (INR)

Values outside the normal range will be categorized as H (above the normal range) or L (below the normal range) based on the central laboratory's normal reference range. Laboratory data will be summarized by visit using standard descriptive statistics. Changes from baseline will also be summarized.

The following elevations will be assessed:

Predefined Limits of Change (PDLC)
ALT (SGPT) (U/L) Value >3xULN
ALT (SGPT) (U/L) Value >5xULN
ALT (SGPT) (U/L) Value >8xULN
AST (SGOT) (U/L) Value >3xULN
AST (SGOT) (U/L) Value >5xULN
AST (SGOT) (U/L) Value >8xULN
Total Bilirubin (μmol/L) Value >2xULN

Statistical Analysis Plan

Sponsor Name: Poxel
Sponsor Protocol ID: PXL065-003

Predefined Limits of Change (PDLC)

ALP (U/L)	Value >2xULN
-----------	--------------

A listing of patients with elevated PDLC criteria will be produced for Safety set with site 065-S .

7.7.3.2 eGFR

Data for eGFR received from central laboratory will be listed and summarized by treatment group and visit. Local laboratory results will be listed only.

eGFR will be calculated using the chronic kidney disease – epidemiology collaboration (CKD-EPI) formula, as follows [14]:

$$141 \times \min(Scr/\kappa, 1) \alpha \times \max(Scr/\kappa, 1) - 1.209 \times 0.993 \text{Age} \times 1.018 \text{ [if female]} \times 1.159 \text{ [if black]}$$

Scr is serum creatinine (mg/dL), κ is 0.7 for females and 0.9 for males, α is -0.329 for females and -0.411 for males, min indicates the minimum of Scr/ κ or 1, and max indicates the maximum of Scr/ κ or 1.

CKD stages are defined as:

- CKD stage 1 (eGFR ≥ 90 mL/min/1.73m 2)
- CKD stage 2 (eGFR ≥ 60 to < 90 mL/min/1.73m 2)
- CKD stage 3a (eGFR ≥ 45 to < 60 mL/min/1.73m 2)
- CKD stage 3b (eGFR ≥ 30 to < 45 mL/min/1.73m 2)
- CKD stage 4 (eGFR ≥ 15 to < 30 mL/min/1.73m 2)
- CKD stage 5 (eGFR < 15 mL/min/1.73m 2)

Shift tables from baseline will be presented at each post-baseline visit showing the number of patients per treatment group with each populated CKD stage for the Safety set.

eGFR data will be summarized by treatment group and visit using standard descriptive statistics, changes from baseline will also be summarized. Summary tables will be produced for the Safety set.

A listing of eGFR data will be produced for the Safety set with site 065-S .

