### ***Target disease exclusions***

5. Evidence of another form of active liver disease including but not limited to viral hepatitis, autoimmune hepatitis, alcoholic disease, cholestatic liver disease, Wilson's disease, Alpha-1-antitrypsin deficiency, hemochromatosis or drug induced liver injury (DILI)
6. Aspartate aminotransferase (AST) or alanine aminotransferase (ALT) > 200 IU/L during Screening Period
7. Evidence of hepatic impairment during Screening Period as defined by any of the following parameters:
  - a. Total bilirubin (TBL)  $\geq$  1.3 mg/dL unless diagnosis of Gilbert's disease
  - b. Serum albumin < 3.5 g/dL
  - c. International Normalized Ratio (INR)  $\geq$  1.3, except for patients under anticoagulant treatment
  - d. Platelets < 150 G/L
  - e. Hemoglobin < 11 g/dL in females or < 12 g/dL in males
  - f. Evidence of portal hypertension (e.g. ascites, esophageal varices)
8. Bariatric surgery of any kind at any time prior to Randomization Visit (V1)
9. Change in body weight greater than 5% within the last 6 months prior to Randomization Visit (V1)

10. Positive serologic evidence of current infectious liver disease including hepatitis B surface antigen (HBsAg), and/or hepatitis C virus antibody (anti-HCV) with detected circulating ribonucleic acid (RNA) during Screening Period.
11. History of excessive alcohol intake defined by  $\geq 21$  units of alcohol/week in males and  $\geq 14$  units of alcohol/week in females for 2 years prior to Randomization Visit (V1), where a unit of alcohol is equal to 10 g pure alcohol.

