#### 8.3.8.1.4 Adverse Event of Special Interest (AESI)

An AE of Special Interest (AESI, serious or non-serious) is one of scientific and/or medical concern specific to the Sponsor's product or program, for which ongoing monitoring and rapid communication by the investigator to the Sponsor can be appropriate. Such an event might warrant further investigation in order to characterize and understand it. Depending on the nature of the event, rapid communication by the trial Sponsor to other parties (e.g., regulators) might also be warranted.

Even if non-serious, AESI are managed with the same process than SAE:

- notification to the Sponsor within 24h following investigator awareness
- case to be created and processed in the safety database (including narrative writing) by Safety Provider.

In this study, the following AEs are considered as AESI:

- Heart failure. In case of any event of heart failure, whatever the cause, patients should be referred to a cardiology specialist.
- Pitting edema. In case of occurrence of pitting edema with presence of other suspected signs and/or symptoms of heart failure, patients should be referred to a cardiology specialist.
- Bladder cancer
- Bone fracture
- Drug-induced liver injury (DILI)

**Below are specific recommendations for the management of elevated liver transaminases and/ or total bilirubin to detect and monitor a possible DILI, following FDA guidelines:**

- **For patients with normal liver transaminases and total bilirubin at baseline (Randomization Visit (V1)):**

If patients with normal baseline (Randomization Visit (V1)) liver indices develop new elevations of AST or ALT  $>3 \times$  ULN or TBL  $>2 \times$  ULN values during the study, repeat testing should be performed within 48 to 72 hours. Investigators should also ask the patient if he/she has symptoms.

If there are persistent elevations (ALT or AST  $>3 \times$  ULN or TBL  $>2 \times$  ULN) upon repeat testing, then close observation (as described below) should be implemented and discontinuation of drug should be considered.

Drug should be discontinued, and the patient followed until resolution of symptoms or signs in the following situations:

- ALT or AST  $>8 \times$  ULN
- ALT or AST  $>5 \times$  ULN for more than 2 weeks.

- ALT or AST  $>3 \times$  ULN and (TBL  $>2 \times$  ULN or INR  $>1.5$ , except for patients on anticoagulant treatment)

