- ALT or AST  $>3 \times$  ULN with the appearance of fatigue, nausea, vomiting, right upper quadrant pain or tenderness, fever, rash, and/or eosinophilia ( $>5\%$ ).
- **For patients with elevations in liver transaminases or total bilirubin at baseline (Randomization Visit (V1)):**

If patients with abnormal baseline liver indices develop elevations of AST or ALT  $>2 \times$  baseline or TBL  $>2 \times$  baseline values during the study, repeat testing should be performed within 48 to 72 hours. Investigators should also ask to the patient if he/she has symptoms.

If there are persistent elevations (ALT or AST  $>2 \times$  baseline or TBL  $>2 \times$  baseline values) upon repeat testing, then close observation (as described below) should be implemented and discontinuation of drug should be considered.

Drug should be discontinued, and the patient followed until resolution of symptoms or signs in the following situations:

- If baseline measurements were  $<2 \times$  ULN, discontinue if ALT or AST increases to  $>5 \times$  baseline measurements.
- If baseline measurements  $\geq 2 \times$  ULN ( $\leq 200$  IU/L as per eligibility requirements), discontinue if ALT or AST increases to  $>3 \times$  baseline measurements.
- If baseline measurements  $\geq 5 \times$  ULN ( $\leq 200$  IU/L as per eligibility requirements), discontinue if ALT or AST increases to  $>2 \times$  baseline measurements.
- Discontinue if ALT or AST increase  $>2 \times$  baseline measurements AND the increase is accompanied by a concomitant increase in TBL to  $>2 \times$  baseline measurements or the INR concomitantly increases by  $>0.2$ , except for patients on anticoagulant treatment.
- For any patients who present with a constellation of syndromes indicative of liver disease as per the Investigator's overall assessment (i.e. fatigue, nausea, vomiting, right upper quadrant pain or tenderness, fever, rash, and/or eosinophilia [ $>5\%$ ]).

- **Close observation for suspected DILI includes the following:**

- Repeating liver enzyme (ALT, AST, and ALP) and TBL tests 2 or 3 times weekly. The frequency of repeat testing can decrease to once a week or less if abnormalities stabilize or the IMP has been discontinued and the patient is asymptomatic.
- Obtaining a more detailed history of symptoms and prior or concurrent diseases.

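### The SAP's liver flags are single-test multiples of ULN, so for patients with elevated baseline they cannot tell a stable high value from a rise, and they miss some signals that the protocol itself defines

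*SAP*

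**What the plan says.** SAP section 7.7.3.1 lists eight predefined limits of change (PDLC). ALT has three levels, from "ALT (SGPT) (U/L) Value >3xULN" to "ALT (SGPT) (U/L) Value >8xULN", with one at 5 times ULN between them. AST has the same three, starting at "AST (SGOT) (U/L) Value >3xULN". Total bilirubin and ALP each have one level, above 2 times ULN. No limit refers to baseline, none combines two tests, and INR has none. The section does not say whether the flags are confined to post-baseline values. The output named is: "A listing of patients with elevated PDLC criteria will be produced for Safety set with site 065-S". For the laboratory panel in general the section adds: "Changes from baseline will also be summarized".

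Protocol section 8.3.8.1.4 has two sets of liver rules. One covers patients whose normal baseline "liver indices develop new elevations of AST or ALT" above 3 times ULN, or bilirubin above 2 times ULN. The other begins "If patients with abnormal baseline liver indices develop elevations of AST or ALT" and works in multiples of the patient's own baseline. Each set includes a combined criterion of ALT or AST with bilirubin or INR, with an exception for patients on anticoagulants.

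The second set will be used. The entry limit, in the protocol's target disease exclusions, is "Aspartate aminotransferase (AST) or alanine aminotransferase (ALT) > 200 IU/L during Screening Period", so values up to 200 IU/L are admitted. SAP section 7.6.2.4 plans an endpoint in patients whose liver enzymes are above the reference range at baseline.

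**The concern.** Part of this population is expected to start with raised transaminases. In such a patient, a flag based on ULN alone describes the level, not the change. A patient who enters high and stays there is flagged. One who enters slightly above normal and more than doubles may not be. The protocol avoids this by switching to baseline multiples for these patients and by treating a transaminase rise with bilirubin or INR as a separate signal. The SAP does not carry either element into its flags.

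At stake is whether individual liver signals can be counted by dose. Safety is the first of the secondary objectives, and protocol section 4.2 says that the trial is meant to inform the doses for Phase 3.

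**Working it through.** The plan gives no figure to reproduce. The check converts each protocol level to a multiple of ULN and asks whether an SAP flag fires there.

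**Inputs**
- SAP flags (7.7.3.1): ALT or AST above 3, 5 or 8 × ULN; bilirubin or ALP above 2 × ULN.
- Protocol, elevated baseline (8.3.8.1.4): repeat test when ALT, AST or bilirubin exceeds 2 × baseline.
- Protocol, elevated baseline, ALT/AST-only stopping levels: above 5 × baseline if baseline is below 2 × ULN; above 3 × baseline from 2 × ULN; above 2 × baseline from 5 × ULN. A baseline of 5 × ULN or more falls in both upper tiers. I used 2 × baseline there because it is reached first.
- Protocol, elevated baseline, combined criterion: ALT or AST above 2 × baseline with bilirubin above 2 × baseline, or with an INR increase above 0.2.
- Entry cap: 200 IU/L.
- ULN for ALT and AST: not in the documents. I assume 30 to 60 IU/L.

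**1. Normal baseline.** The protocol's single-test levels are 3, 5 (for more than two weeks) and 8 × ULN for ALT or AST, and 2 × ULN for bilirubin. Apart from the duration condition, the SAP levels are the same.

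**2. Stable high values.** The cap as a multiple of ULN is 200 / ULN:
- ULN 30: 6.7
- ULN 40: 5.0
- ULN 50: 4.0
- ULN 60: 3.3

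An unchanged patient at the cap exceeds 3 × ULN whenever ULN is below 200 / 3 = 66.7 IU/L. The protocol's tier for baselines of at least 5 × ULN can be populated within the cap only if ULN is at most 200 / 5 = 40 IU/L. A patient above that level trips the 3 × and 5 × flags with no change.

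**3. Rises from an elevated ALT or AST** (all in × ULN, so no assumed ULN is needed)

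| Baseline | Repeat-test level (2 × baseline) | Rise left unflagged | ALT/AST-only stopping level | SAP levels reached at stopping |
|---|---|---|---|---|
| 1.1 | 2.2 | 2.2 to 3.0 | 5 × 1.1 = 5.5 | 3, 5 |
| 1.2 | 2.4 | 2.4 to 3.0 | 5 × 1.2 = 6.0 | 3, 5 |
| 1.4 | 2.8 | 2.8 to 3.0 | 5 × 1.4 = 7.0 | 3, 5 |
| 1.5 | 3.0 | none | 5 × 1.5 = 7.5 | 3, 5 |
| 2.0 | 4.0 | none | 3 × 2.0 = 6.0 | 3, 5 |
| 3.1 | 6.2 | none, but flagged when unchanged | 3 × 3.1 = 9.3 | 3, 5, 8 |

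The repeat-test trigger can be missed when baseline is below 3 / 2 = 1.5 × ULN. The stopping levels are not missed: for a transaminase that was itself elevated, they all lie above 5 × ULN. There is one edge case. If a patient is in the elevated group because of another test and has ALT below 3 / 5 = 0.6 × ULN, then 5 × baseline is below 3 × ULN and no flag fires.

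**4. Bilirubin.** A value above 2 × baseline can lie below 2 × ULN whenever baseline is below 1 × ULN. At a baseline of 0.5 × ULN, the protocol's level is 1.0 × ULN.

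**5. Combined criterion, elevated baseline.** Take ALT from 1.2 to 2.5 × ULN and bilirubin from 0.5 to 1.1 × ULN.
- ALT: 2.5 / 1.2 = 2.08 × baseline, above 2, so the protocol condition is met; 2.5 is below 3, so no SAP flag.
- Bilirubin: 1.1 / 0.5 = 2.2 × baseline, above 2, so the protocol condition is met; 1.1 is below 2, so no SAP flag.

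The patient meets the combined criterion and does not enter the PDLC listing, whatever the ULN.

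**The case against.** The strongest reply is that the flags are a small part of the liver evaluation. The SAP plans baseline-adjusted repeated-measures models of ALT, AST, GGT and ALP by arm (7.6.2.3), normalization rates in patients elevated at baseline (7.6.2.4), and summaries of the panel, including bilirubin and INR, by visit with change from baseline (7.7.3.1). Drug-induced liver injury and adverse events leading to discontinuation are tabulated by arm (7.7.2). All panel values are listed, and with about 30 patients per arm individual review is feasible. The protocol's rules are also recommendations for managing patients, which analysis flags need not copy in full.

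Much of this stands. A reader might infer that the liver comparison between doses is uninformative. The documents do not support that: the group-level analyses are adjusted for baseline and reported by arm. Nor do they support saying that the flags omit the protocol's signals in general, given the agreement in steps 1 and 3. It would also go too far to say that transaminases and bilirubin can never be viewed together. When both exceed their ULN levels, a reader can match the entries for one patient. A patient actually taken off treatment for a laboratory finding should also appear as an adverse event under the protocol's reporting rule.

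The narrower gap remains. Group means do not identify individual outliers. Only confirmed drug-induced liver injury is reported as an event of special interest, and laboratory abnormalities are generally not adverse events unless they have consequences. A patient who trips no flag is not in the PDLC listing to be matched. Finding that patient means computing ratios by hand from the full laboratory listing, and no count by arm would result.

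**Conclusion.** The point holds as a limited gap in individual-level liver reporting, and it is a cheap improvement. For patients with elevated baseline, the flags cannot separate a stable high value from a rise. They also miss three kinds of signal that the protocol defines: ALT or AST above twice baseline when baseline is below 1.5 × ULN, bilirubin above twice a normal baseline, and some cases meeting the combined criterion. No combined criterion is defined for either baseline group, and nothing is counted by arm.

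The missed-signal results are in multiples of ULN and do not depend on its value. The stable-patient result does, and is shown for an assumed ULN of 30 to 60 IU/L. The number of patients affected cannot be stated, because the documents give neither the laboratory's ULN nor a baseline distribution. A reader might also infer that pre-treatment values will be flagged; the SAP is silent on that, and the layout of the listing is not visible. This concerns analysis flags only and takes no view on which clinical threshold is right.

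**What to change.** In SAP section 7.7.3.1:

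1. State that the PDLC flags apply to post-baseline values, and keep the existing levels.
2. Add analysis flags that mirror the criteria already in protocol section 8.3.8.1.4. For patients with elevated baseline, use the protocol's baseline multiples for ALT, AST and bilirubin, with its tiers by baseline level, and state how the overlap of the two upper tiers is read.
3. Add a concurrent flag for ALT or AST with bilirubin or INR in both baseline groups, each using the protocol's own definition for that group and its anticoagulant exception. Define concurrent, for example as the same sampling date.
4. Tabulate the number of patients meeting each flag by treatment arm in the Safety Set, alongside the listing.

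The central laboratory panel already includes ALT, AST, bilirubin and INR, concomitant medications are already coded, and SAP section 7.6.2.4 already derives the elevated-baseline subset for each enzyme. The cost is a few derived variables and one table. No data collection, visit or clinical rule changes.
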